The PA intervention is a 5 session online intervention that teaches 8 skills for increasing the frequency of positive emotions: 1) noting daily positive events²⁵⁻²⁸ 2) capitalizing on or savoring positive events;²⁹⁻³⁰ 3) gratitude;³¹⁻³³ 4) mindfulness;³⁴⁻³⁷ 5) positive reappraisal;³⁸⁻⁴⁵ 6) focusing on personal strengths;^{42-43,49-52} 7) setting and working toward attainable goals;^{53-54,55-58} and 8) small acts of kindness.⁵⁹⁻⁶³ The skills are presented over the course of 5 weeks. A week will consist of 1-2 days of didactic material and several days of brief, real-life skills practice and reporting, with each day's "home practice" taking approximately 20-30 minutes to complete. Patients cannot skip ahead, but they can return to old lessons or exercises if they choose. Most exercises are done in a "diary" format in which patients' past responses are displayed next to their new ones, so that every time the patient visits that exercise they see their growing list of past positive experiences. Patients will be permitted up to 8 weeks to complete this self-guided intervention to account for normal interruptions and unexpected delays in life.

Acceptability Interview. Research staff will conduct a 30-minute audio-recorded, post-intervention phone interview with all patients approximately one week after the intervention is complete to gather acceptability data. The semi-structured interview includes questions where participants rank the skill sessions in terms of favorite topics, the likelihood of referral to others (a friend or someone diagnosed with cancer) and the likelihood of practicing learned skills. There is also a section with open-ended questions, including questions about participant experiences with use of the website and home practice exercises

Patient Incentives. Each patient will be paid \$10 for each completed assessment for a maximum of \$30. Patients will be paid in full upon completion of the study via virtual gift card.

ENHANCING MANAGEMENT OF PATIENT REPORTED OUTCOMES WITH
EMOTION REGULATION (*EMPOWER*)
Comprehensive Cancer Center of Wake Forest University (CCCWFU)
CCCWFU 99516

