Fidelity Monitoring. Whether patients understood and remember the intervention content will be assessed via multiple-choice "quiz" questions within each lesson. If patients are not able to answer a question, it will trigger a review of the relevant material (patients can also choose to review past material at any time). How frequently patients visit the website and how many times they complete the daily practice exercises for each skill will also be recorded. This information can be used in "dose-response" analyses to determine whether greater exposure to the exercises leads to stronger intervention effects. Patient progress will be monitored during the study and patients who appear to be having trouble or are disengaging from the intervention will be contacted. Our experience indicates that even very brief human contact can increase patients' commitment to the intervention. Patients will receive an email or phone call from a study staff member if they fail to visit the website more than 3 days in a week. Patients who cannot be reached or who do not resume visiting the website but also don't ask to leave the study will be re-contacted once per week for 3 weeks. After that they will be counted as non-completers, though we will still try to contact them to obtain post-intervention measures. Patients who do not reach the final lesson at the end of 8 weeks will also be considered non-completers and will be asked to take the post-intervention measures at that time.

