6.1 Analysis of Primary Objective

Accrual will be estimated as the number of patients accrued divided by the number of months of accrual. A 95% confidence interval for the monthly accrual rate will be calculated based on the Poisson distribution. The refusal rate will be estimated as the number of patients who refuse to participate divided by the number eligible. Retention will be primarily defined as the proportion of patients who provide 8 week and 12 week data. Patients who discontinue the intervention (refuse phone calls) but complete the outcome assessments will be counted in the numerator for calculating retention. Retention estimates will be calculated overall and by site. Adherence to the intervention will be calculated as the number of intervention sessions completed, the frequency of completing exercises, and number of website visits. We will calculate and report the mean adherence across all individuals as well as the proportion of patients who completed three or more sessions. Several measures will be used to quantify acceptability, including quantitative measures and interview. Means and the proportion responding affirmatively to the highest two responses for each question will be combined and exact 95% CIs will be calculated for these estimates. In addition, [name] and [name] will review open-ended (written) feedback and audio-recordings of phone interviews to identify meta-themes and determine saturation of concepts.⁷⁸

ENHANCING MANAGEMENT OF PATIENT REPORTED OUTCOMES WITH
EMOTION REGULATION (*EMPOWER*)
Comprehensive Cancer Center of Wake Forest University (CCCWFU)
CCCWFU 99516

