Thank you for taking the time to talk with me today. I just wanted to remind you that this telephone conversation is being recorded for quality assurance purposes. I expect our conversation will be brief, under 30 minutes. Then in one month you'll be hearing from [name of RA] as a reminder to complete your final follow-up assessment.

First, I'd like to ask you a few questions about these sessions and the study so far.

Let's go back through the skills we've covered:

- a. Positive Events
- b. Capitalizing (revisiting positive events)
- c. Gratitude Journal
- d. Formal Mindfulness (breath awareness)
- e. Informal Mindfulness (mindfulness in daily life)
- f. Positive Reappraisal
- g. Personal strengths
- h. Goals
- i. Acts of Kindness

1. Please rank the sessions from your most favorite (1) to least favorite (9):

- _____ Positive Event
- _____ Capitalizing
- _____ Gratitude Journal
- _____ Mindfulness Formal (Breath Awareness)
- _____ Mindfulness Informal (Mindfulness in Daily Activities)
- _____ Positive Reappraisal
- _____ Personal strengths
- _____ Attainable Goals
- _____ Acts of Kindness

2. On a scale of 0 to 10, with 0 being "definitely not" to 10 being "definitely yes", to what extent would you recommend these skills to a friend?

(Please circle your response)

0 1 2 3 4 5 6 7 8 9 10
 Definitely not Definitely

3. To what extent would you recommend this intervention to someone newly diagnosed with cancer? (Please circle your response)

0 1 2 3 4 5 6 7 8 9 10
 Definitely not Definitely

How likely are you to practice the following skills over the next 6 months? (Please circle your response)

4. Positive Event:

0 1 2 3 4 Other ___
 Not at all Once a month Once a week 2-3 times/week Daily

5. Capitalizing:

0 1 2 3 4 Other ___
 Not at all Once a month Once a week 2-3 times/week Daily

6. Gratitude Journal:

0 1 2 3 4 Other ___
 Not at all Once a month Once a week 2-3 times/week Daily

7. Mindful Breath Awareness:

0 1 2 3 4 Other ___
 Not at all Once a month Once a week 2-3 times/week Daily

8. Mindfulness in Daily Activities:

0 1 2 3 4 Other ___
 Not at all Once a month Once a week 2-3 times/week Daily

9. Positive Reappraisal:

0 1 2 3 4 Other ____
Not at all Once a month Once a week 2-3 times/week Daily

10. Personal Strengths:

0 1 2 3 4 Other ____
Not at all Once a month Once a week 2-3 times/week Daily

11. Attainable Goals:

0 1 2 3 4 Other ____
Not at all Once a month Once a week 2-3 times/week Daily

12. Acts of Kindness

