0 1 2 3 4 Other ____
Not at all Once a month Once a week 2-3 times/week Daily

Planning for continued practice

For this last section, I'd like to talk about continued practice of the skills we covered. A basic premise of these coping skills is that they only work if you continue to practice them. Again these skills are like muscles, if you don't exercise them, they aren't likely to work very well. For these skills to be beneficial to you, you need to make them habits.

It sounds like you plan to continue (XX skill from above participant is going to practice most frequently) but are less likely to continue (XX skill from above participant is going to practice less). First let's talk about the one that you plan to continue. What about it is appealing to you? How do you plan to fit it into your day and make it a habit?

How about your least favorite skill? Can you tell me what about that one makes you less likely to try and incorporate it into your life?

One of the interesting things about any new skill is that after a while you might get bored with it or it may stop having the same impact that it had initially. If (skill participant rates as most likely to continue) starts getting old for you, you should go back to the skills and choose another one and increase your practice of that one. Let's talk about (XX skill that participant rated the second most likely to practice) and ways you might be able to incorporate that into your daily life.

Questions about website usage:

Can you talk about your experience using the intervention website?

Probe: What features did you like?

What could have been clearer?

What did you think of the at home practice exercises?

If the participant did not progress through all the lessons

Why did you stop at lesson X?

In about four weeks (cite specific dates), I will email you the final online questionnaire for the study. This will mark the end of your participation in the study.

Are there any questions I can answer for you now?

Thank you again for your time and participation in this study. We really appreciate it!

Hang up.

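### The interview asks early stoppers to rank and rate skills they were never taught, so later skills can look less acceptable partly because fewer patients reached them

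*Combined protocol and SAP*

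**What the plan says.** Section 4.2 (Study Design) fixes the order of the lessons: "Patients cannot skip ahead, but they can return to old lessons or exercises if they choose". It plans a "post-intervention phone interview with all patients approximately one week after the intervention is complete". Under Fidelity Monitoring it foresees early stopping: "Patients who do not reach the final lesson at the end of 8 weeks will also be considered non-completers". The same paragraph has the study record how often each patient completes the practice exercises for each skill.

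The phone interview script in Appendix C opens with "Let's go back through the skills we've covered", then prints one fixed list of nine items (formal and informal mindfulness are listed separately). Question 1 reads "Please rank the sessions from your most favorite (1) to least favorite (9". Questions 4 to 12 ask "How likely are you to practice the following skills over the next 6 months", with one item per skill on a scale from 0 (not at all) to 4 (daily), plus a blank labelled 'Other' whose meaning and scoring are not given. The only branch for early stoppers, "If the participant did not progress through all the lessons", comes after all the ranking and rating, and asks why they stopped.

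Acceptability is among the primary outcomes in Section 5.1. Section 6.1 analyses it as follows: "Means and the proportion responding affirmatively to the highest two responses for each question will be combined", with exact 95% confidence intervals. It names no denominator for the skill items and does not refer to lessons reached.

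**The concern.** A patient who stopped at the third lesson has not been taught what comes later, yet the script asks that patient for a place in the ranking and a practice rating for each later skill. A rank of 9 or a rating of 0 can then mean either that the skill was tried and disliked or that it was never seen, and the answer alone does not show which.

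Because the order is fixed, not reaching a skill goes with its position in the programme. Any tendency to mark unseen skills low falls on the later skills and leaves the first ones untouched. Unlike sampling error, such a shift does not shrink with more patients. The follow-up about the least favourite skill could also lead an early stopper to explain dislike of something never taught, and those recordings feed the theme review in Section 6.1.

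At stake is the skill-level part of a primary outcome. It would be natural to use it when refining the programme, although the protocol does not say that it will be so used.

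**Working it through.** **Does the problem arise under the plan as written?** Four things must hold together.

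1. Early stoppers have not seen the later skills: Section 4.2 rules out skipping ahead.
2. Early stoppers are interviewed: Section 4.2 says all patients, and the script has a branch for those who did not finish.
3. They receive the same items: the list, the ranking and the nine ratings are fixed, with no skip rule before them.
4. The analysis does not separate them: Section 6.1 works question by question and does not mention exposure.

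All four hold. Questions 2 and 3, on recommending the programme, are not skill-specific and are untouched by this mechanism.

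**The plan's own precision.** The Power and Sample Size section gives ±12.7% for a proportion at 60 patients and ±14.1% after 20% dropout (48 patients). Check: 1.96 × √(0.25/60) = 12.65%, and 1.96 × √(0.25/48) = 14.14%. Both reproduce.

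**Size of the possible shift.** Let u be the share of interviewees who did not reach a skill. Let p be the top-two proportion (practice 2 to 3 times a week or daily) among those who reached it, and q the same proportion among those who did not. Then

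- pooled proportion = (1 − u)p + uq
- shift = u(p − q)

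The documents give none of u, p or q. I assume u from 10% to 40%, p of 60% or 80%, and q from 0 (all give the lowest rating) up to p (answered like seen skills).

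**Ranks.** Suppose early stoppers saw the first k of the nine items and put the rest last, with ranks otherwise random. Within this group the mean rank is (k + 1)/2 for seen items and (k + 10)/2 for unseen items, a difference of 4.5 whatever k is. Over all interviewees the gap is 4.5u.

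| u | Pooled, p = 60%, q = 0 | Pooled, p = 60%, q = 30% | Pooled, p = 80%, q = 0 | Rank gap | Reached, of 60 | Worst-case half-width, reached only |
|---|---|---|---|---|---|---|
| 10% | 54% | 57% | 72% | 0.45 | 54 | 13.3% |
| 20% | 48% | 54% | 64% | 0.90 | 48 | 14.1% |
| 30% | 42% | 51% | 56% | 1.35 | 42 | 15.1% |
| 40% | 36% | 48% | 48% | 1.80 | 36 | 16.3% |

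With q = p the pooled figure stays at p for every u. The last column is 1.96 × √(0.25/n).

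**Against the plan's precision.** At u = 20% and q = 0 the shift is 0.2p. It exceeds 12.65 points only if p is above 0.1265/0.2 = 63%. Against the exact half-width at 48 patients and 50% (14.8%), p must be above 0.148/0.2 = 74%. So 12 points (p = 60%) lies below both benchmarks and 16 points (p = 80%) above both.

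**The case against.** The best reply is that the instrument is looser than it looks and the data can be repaired. Section 4.2 calls the interview semi-structured; the lead-in speaks of skills covered; the interviewer evidently knows where the patient stopped; and an interviewer could write 'not reached' in the 'Other' blank. Sessions completed and practice counts per skill are recorded, so unseen items can be identified afterwards, and removing them from a ranking keeps the order of the rest. Section 6.1 leaves the denominator open; it does not say that everyone who answered is included.

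Much of this stands. It is fair that questions 4 to 12 do not strictly force an answer, and that the damage is largely recoverable. But an undefined blank and interviewer discretion are not a rule, handling may differ between interviewers, and the plan nowhere says the repair will be made. Question 1 as printed asks for a full ranking.

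A second reply is that a low rating from someone who never reached a skill may be a true statement about uptake of the programme as delivered. That is a legitimate but different quantity, and the pooled figure does not separate it from liking among those taught the skill.

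Third, few early stoppers may be interviewed, since those who cannot be contacted drop out altogether. The plan's only 20% is study dropout, not the share of interviewees who missed a skill. This is why the size cannot be fixed.

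A reader might infer that later skills will score worse solely because fewer patients reached them, that the artefact is larger than the confidence interval, or that late skills will be cut for this reason. The documents support none of these. They do not say how unseen skills would be answered or how many interviewees stop early, and no passage makes the skill ratings a rule for keeping or dropping a skill.

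**Conclusion.** The concern holds as a gap in the questionnaire and its analysis: followed as written, the script mixes 'never taught' with 'tried and not liked' in a primary outcome, and the mixing grows with a skill's position in the programme. Later skills can look less acceptable partly for that reason.

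At u = 20% the downward shift in a top-two proportion runs from zero (unseen skills answered like seen ones) to 12 points at p = 60% or 16 points at p = 80% (all unseen skills given the lowest rating). These inputs are assumed. Whether the shift is large beside the plan's stated precision depends on them, so no claim that it exceeds the confidence interval should be made.

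No sample-size figure is wrong. The fault is correctable and does not threaten the study, but it should be corrected before skills are compared with one another.

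**What to change.** **Script.** Add a 'not reached' code to questions 1 and 4 to 12, and ask patients to rank and rate only the skills they reached. Say what 'Other' means and how it is scored.

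**Section 6.1.** Define 'reached' from the sessions completed and the per-skill practice counts already recorded. A practice count of zero does not by itself show that a lesson was not seen, so the definition should state which source decides. Report each skill's estimate among patients who reached it, with its n and the share not reached.

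**Comparing skills.** Patients who reach later skills are likely to be the more engaged ones, so estimates restricted to those who reached a skill may flatter the later skills. Compare skills with one another only among patients who reached all lessons, so that every skill has the same denominator.

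**Interviews already held.** Section 6.3 reports 18 patients recruited, so some interviews may exist. They can be recoded from the exposure data, with ranks recomputed among reached skills.

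**Cost.** One response code, one merge with data already planned, and a smaller n for later skills. If 20% of 60 did not reach a skill, its worst-case half-width is about 14.1% instead of 12.7%.

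### The phone interview asks its open-ended evaluation questions after staff promote continued practice, and no probe asks what was disliked or burdensome about the website or home practice

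*Combined protocol and SAP*

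**What the plan says.** Section 4.2 describes a recorded, semi-structured telephone interview of 30 minutes, held by research staff about a week after the intervention to collect acceptability data. It says that the open-ended part covers patients' experience of the website and of the home practice. Section 5.1 lists acceptability among the primary outcomes. Section 6.1 plans a review of written open-ended feedback and of "audio-recordings of phone interviews to identify meta-themes and determine saturation of concepts".

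The script in Appendix C has three parts after the introduction:

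- **Items 1-12:** a ranking of the skills, two 0-10 recommendation items and nine items on likely future practice.
- **Planning for continued practice:** introduced with "For this last section". Staff say "A basic premise of these coping skills is that they only work if you continue to practice them" and "For these skills to be beneficial to you, you need to make them habits". They ask what appeals about the skill the patient means to keep up, and what puts the patient off the least favorite one. If a skill goes stale, the advice is "you should go back to the skills and choose another one and increase your practice of that one".
- **Questions about website usage:** "Can you talk about your experience using the intervention website", with one probe "What features did you like" and a second on what might have been clearer. A question on the home practice follows and, for patients who did not get through all lessons, one on why they stopped.

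**The concern.** A patient who has just heard the interviewer argue for regular practice, and has been helped to plan it, may find it harder to call the exercises tedious or to give a blunt reason for quitting. The documents lend this some plausibility: in Section 4.2, under Fidelity Monitoring, the investigators report that even short human contact can raise commitment to the intervention. Here, contact meant to build commitment comes immediately before the request for an evaluation.

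The gap in the probes adds to this. Workload is an obvious topic for an intervention with 20-30 minutes of home practice a day, yet the home-practice question has no probe and the website probes do not reach burden.

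The pilot is meant to prepare a full-scale randomized trial. Complaints that go unvoiced here would carry over into that trial's design. More interviews would not help, because every interview held in the scripted order shares the same order effect.

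**Working it through.** No arithmetic applies. The check is to read the script in sequence and set it against the stated use of the answers.

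**Order**

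1. Items 1-12 come first. The numeric ratings are therefore collected before any promotion of practice.
2. The planning section comes second and is announced as the last one. It contains the statements on practice and habits, and ends with coaching on a further skill.
3. The website block comes third, so the section announced as last is not last. The topics of this block (website and home practice) are the ones Section 4.2 names for the open-ended acceptability questions.

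**Invitations to criticise**

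| Topic | What the script asks | Asked of | Relative to the practice talk |
|---|---|---|---|
| Skills | Ranking down to least favorite | All | Before |
| Skills | What puts the patient off the least favorite skill | All | During |
| Website | Neutral opening, then liked features and clarity | All | After |
| Home practice | Neutral question, no probe | All | After |
| Stopping | Why the patient stopped | Those who did not progress through all lessons | After |

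The script thus gives several openings for negative views. What it lacks is any probe on dislike or burden for the website or for home practice.

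**Reach**

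- The website and home-practice questions go to every patient interviewed, at most 60 under the planned sample size.
- The stopping question goes only to those who did not progress through all lessons. The documents do not give that number.
- Section 6.3 reports 18 patients recruited so far, at Northwestern. If those 18 count toward the 60, are the only patients recruited, and have all been interviewed in the present order, then 60 - 18 = 42 patients remain who could be interviewed with a revised script. More would remain if some of the 18 are still to be interviewed, and fewer if the other site has also begun.

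**The case against.** The strongest case against is that this is a matter of preference. The interview is semi-structured, so a good interviewer can follow up on burden unprompted. The planning section is not pure advocacy: it concedes that a skill may become boring or lose its effect, and it asks why the patient is unlikely to use the least favorite one. That gives some licence to be negative. The talk concerns future use of skills, so it is not obvious why it would suppress remarks about website features. Disengagement is also recorded objectively through website visits and completed exercises. Calling the planning talk the last section may be no more than a slip of wording.

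Much of this stands, and it narrows the point to the home-practice and stopping answers, where the link to the talk is direct. It does not remove the point. Usage logs show that a patient stopped, not why. Leaving burden to the interviewer's initiative makes coverage uneven across calls.

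A reader might infer that the script never invites criticism. It does: through the clarity probe, the least-favorite-skill question and the stopping question. A reader might also infer that the acceptability results as a whole are compromised. They are not: the numeric items come first, and written feedback also feeds the themes, although the Appendix C text available shows no form for it.

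**Conclusion.** The order problem and the missing probe are both plain on the page, and both are worth correcting. The consequence is a risk to part of the qualitative evidence on one primary outcome, most plausibly the home-practice answers and the reasons given by patients who stopped early. That rests on one assumption: that people speak less critically of an activity just after the interviewer has urged it on them.

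It would be tempting to conclude that the themes are in fact tilted favourably. The documents do not support that. They show a sequence that could produce such a tilt, and they contain nothing from which its size or direction could be established. The case for acting is that the change is nearly free and keeps the coaching intact.

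**What to change.** - Move the whole block of website questions, including the home-practice and stopping questions, to directly after item 12 and before the planning section. The planning talk then really is the last section, as its opening words say.
- Add a neutral probe on what the patient disliked or found burdensome, asked once about the website and once about the home practice.
- In the theme analysis, flag interviews held in the present order, so that any theme on burden or stopping can be compared between the two sets.

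The cost is a script revision and about one more minute per call. The planning talk refers back to items 4-12, so the gap between them grows slightly; the interviewer can read the recorded answers back. Interviews already held cannot be changed, and the flag is the only remedy for those.
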